2.4. Demographic and Baseline Variables

Demographic and baseline characteristics include:

- Age
- Sex
- Race
- Ethnicity
- Height (in cm)
- Weight (in kg)
- Body Mass Index
- Duration of CeD
- Duration of gluten-free diet (GFD)
- CeD Serology at diagnosis
- Histology at diagnosis

2.5. Safety Endpoints

Safety will be assessed by medical history, vital signs, clinical laboratory tests, and the reporting of AEs, in all participants who received any portion of study intervention.

Unscheduled safety assessments may be performed at any time during the study to assess any perceived safety concerns. Investigators and Clinicians will review individual participant data throughout the conduct of the study to ensure participants' wellbeing.

2.5.1. Adverse Events

Incidence and severity of TEAEs is the Secondary endpoint.

An adverse event (AE) is considered TEAE to a given treatment if the event start date is on or after the treatment period start date and before end of study.

The CTCAE displays Grades 1 through Grade 5 with unique clinical descriptions of severity for each AE based on below general guideline:

- **Grade 1:** Mild; asymptomatic or mild symptoms; clinical or diagnostic observations only; intervention not indicated.
- **Grade 2:** Moderate; minimal, local or noninvasive intervention indicated; limiting age appropriate instrumental activities of daily living (ADL).
- **Grade 3:** Severe or medically significant but not immediately life-threatening; hospitalization or prolongation of hospitalization indicated; disabling; limiting selfcare ADL.
- **Grade 4:** Life-threatening consequences; urgent intervention indicated.
- **Grade 5:** Death related to AE.

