**Overall Design:**

Study KAN-101-03 is a multi-center, double-blind, placebo-controlled Phase 2a study to examine whether KAN-101 confers protection from GC-induced histological changes in the duodenum and to further evaluate the safety/tolerability of KAN-101 in adult participants ( $\geq 18$  years) with CeD. Fifty-two participants (26 participants per arm) will be randomized 1:1 to the following arms: **0.6 mg/kg KAN-101 (Arm 1)** and **Placebo (Arm 2)**. This study comprises 4 periods:

**Screening period:** The study screening period is  $\leq 42$  days. During the screening period, eligibility will be confirmed by EGD with duodenal biopsy. The EGD with biopsy will only be performed once all other inclusion criteria are fulfilled. Histology results must be received prior to dosing to confirm eligibility.

**Treatment period:** The study treatment period is 7 days (Day 1 to Day 7). Study intervention will be administered to enrolled participants in the clinic intravenously (IV) on Day 1, Day 4, and Day 7. Post infusion each treatment day, participants will be monitored in the clinic for at least 4 hours for adverse reactions.

**GC:** Participants will undergo a 2-week GC in which they will ingest 9 g/day of gluten protein in the form of 12 g vital wheat gluten. All participants will return to the clinic on Day 15 for the first day of GC. The Day 15 GC will be performed in the clinic under supervision and blood samples will be collected at least 5 minutes prior to GC and 4 hours after the completion of the Day 15 GC for biomarker assessment. Materials will be sent home with the participant to complete the GC daily for the next 2 weeks (through Day 28). The study site will call the participant on Day 16 and Day 21 to collect data on any AEs or CM over the telephone. Symptom monitoring and compliance with the GC will be conducted via eDiary.

**Observation and Follow-up period:** Participants will be observed and followed for safety for the duration of the study (42 days [Day 1 to Day 42]). The second EGD with duodenal biopsy will be conducted on Day 29. Participants will return to the clinic on Day 42 for a final follow-up visit including safety assessment and labs, celiac serology, and exploratory biomarker sample collections.

If participants are unable to return to the clinic for protocol-specified visits, alternative methods for safety assessments and data collection may be employed to ensure the safety of the trial participants when appropriate.

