### 2.3.1. Risk Assessment

Potential Risk of Clinical Significance	Summary of Data/Rationale for Risk	Mitigation Strategy
Study Intervention(s) [KAN-101 and placebo]		
Potential for exacerbation of gastrointestinal symptoms associated with CeD, which may include and are not necessarily limited to AEs of headache, dizziness, fatigue/lethargy, nausea, vomiting, abdominal pain, diarrhea, constipation, skin rash, and abdominal tenderness.	The potential risks are based on the mechanism of action of KAN-101 and other similar therapeutic investigational immunomodulatory therapies in CeD (Daveson et al, 2017; Truitt et al, 2019).	AEs and clinical laboratory results will be monitored on an ongoing basis and managed according to established standard of care.
Use of a placebo arm.	The use of a placebo represents a potential risk.	Participants who experience worsening of CeD may discontinue from the study and may receive standard of care treatment at the investigator's discretion.
IV infusions will be administered over 30 minutes every 3 days during study treatment period.	IRR are known risks associated with IV infusions.	IRR will be monitored and specific guidance on acute and prophylactic treatment of IRRs and recommendations for future infusions of KAN-101 are provided in Appendix 9 .
Potential hypersensitivity reactions may occur and include skin reaction, mucosal tissue reaction, respiratory reaction, GI reactions, and CV reactions.	Similar to other biologic molecules.	Participants will be closely monitored on site for 4 hours post infusion for signs of any reaction.
KAN-101 is a liver targeting agent.	Although FIH Study KAN-101-01 and nonclinical data show that KAN-101 had no significant impact on the liver (eg, liver enzyme levels and histopathology), KAN-101's potential impact on liver enzymes and bilirubin will continue to be evaluated in the clinical setting.	Transaminase, ALP and total bilirubin levels will be closely monitored and are included in safety laboratory assessments. Participants with ALT, AST, or ALP $>1.5 \times$ ULN are not eligible for enrollment in KAN-101-03.

CONFIDENTIAL

CT02-GSOP Clinical Protocol Template Phase 1 2 3 4 (14 April 2023)

Page 31

Potential Risk of Clinical Significance	Summary of Data/Rationale for Risk	Mitigation Strategy
		Participants considered to have a potential case of Hy's law will lead to a cessation of clinical dosing and participant will be followed to resolution.

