#### **8.3. Safety Assessments**

Safety will be assessed through the monitoring of AEs, clinical signs and symptoms, vital signs and clinical laboratory evaluations.

All participants will be monitored continuously for AEs from screening until the safety follow-up visit on Day 42. AE severity will be assessed using the NCI CTCAE v6.0 or higher (see [Appendix 10](#)). The DSMB will review cumulative safety data periodically. Any Grade 4 AEs assessed as related to study drug will result in notification of the regulatory agencies in parallel with the DSMB.

Participants will be monitored in the clinic for at least 4 hours following IV study drug administration for IRR (see [Appendix 9](#)).

In relation to participant safety during the COVID-19 pandemic, current national laws and local recommendations should be strictly adhered to during the study.

Planned time points for all safety assessments are provided in the SoA. Unscheduled safety measurements may be obtained at any time during the study to assess any perceived safety issues.

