#### **8.4.1. Time Period and Frequency for Collecting AE and SAE Information**

The time period for actively eliciting and collecting AEs and SAEs (“active collection period”) for each participant begins from the time the participant provides informed consent, which is obtained before undergoing any study-related procedure and/or receiving study intervention, through and including a minimum of 28 calendar days, except as indicated below, after the last administration of the study intervention.

Follow-up by the investigator continues throughout the active collection period and until the AE or SAE or its sequelae resolve or stabilize at a level acceptable to the investigator.

When a clinically significant AE remains ongoing at the end of the active collection period, follow-up by the investigator continues until the AE or SAE or its sequelae resolve or stabilize at a level acceptable to the investigator and the sponsor concurs with that assessment.

For participants who are screen failures, the active collection period ends when screen failure status is determined.

If the participant withdraws from the study and also withdraws consent for the collection of future information, the active collection period ends when consent is withdrawn.

If a participant permanently discontinues or temporarily discontinues study intervention because of an AE or SAE, the AE or SAE must be recorded on the CRF and the SAE reported using the CT SAE Report Form.

Investigators are not obligated to actively seek information on AEs or SAEs after the participant has concluded study participation. However, if the investigator learns of any SAE, including a death, at any time after a participant has concluded study participation, and they consider the event to be reasonably related to the study intervention, the investigator must promptly report the SAE to Pfizer Safety using the CT SAE Report Form.

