## 10.3. Appendix 3: Adverse Events: Definitions and Procedures for Recording, Evaluating, Follow-Up, and Reporting

### 10.3.1. Definition of AE

AE Definition

• An AE is any untoward medical occurrence in a patient or clinical study participant, temporally associated with the use of study intervention, whether or not considered related to the study intervention.

• Note: An AE can therefore be any unfavorable and unintended sign (including an abnormal laboratory finding), symptom, or disease (new or exacerbated) temporally associated with the use of study intervention.

Events Meeting the AE Definition

• Any abnormal laboratory test results (hematology, clinical chemistry, or urinalysis) or other safety assessments (eg, ECG, radiological scans, vital sign measurements), including those that worsen from baseline, considered clinically significant in the medical and scientific judgment of the investigator. Any abnormal laboratory test results that meet any of the conditions below must be recorded as an AE:

Is associated with accompanying symptoms.

Requires additional diagnostic testing or medical/surgical intervention.

Leads to a change in study dosing (outside of any protocol-specified dose adjustments) or discontinuation from the study, significant additional concomitant drug treatment, or other therapy.

• Exacerbation of a chronic or intermittent preexisting condition, including an increase in either frequency and/or intensity of the condition.

• New condition detected or diagnosed after study intervention administration, even though it may have been present before the start of the study.

• Signs, symptoms, or the clinical sequelae of a suspected drug-drug interaction.

• Signs, symptoms, or the clinical sequelae of a suspected overdose of either study intervention or a concomitant medication. Overdose per se will not be reported as an AE or SAE unless it is an intentional overdose taken with possible suicidal/self-harming intent. Such overdoses should be reported regardless of sequelae.

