#### Follow-Up of AEs and SAEs

- The investigator is obligated to perform or arrange for the conduct of supplemental measurements and/or evaluations, as medically indicated or as requested by the sponsor/Pfizer Safety, to elucidate the nature and/or causality of the AE or SAE as fully as possible. This may include additional laboratory tests or investigations, histopathological examinations, or consultation with other healthcare providers.

- If a participant dies during participation in the study or during a recognized follow-up period, the investigator will provide Pfizer Safety with a copy of any postmortem findings, including histopathology.
- New or updated information will be recorded in the originally submitted documents.
- The investigator will submit any updated SAE data to Pfizer Safety within 24 hours of receipt of the information.

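### The TEAE rule in SAP 2.5.1 goes by start date alone, so a screening AE that worsens after dosing is left out if it stays in its original record

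*SAP*

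**What the plan says.** SAP 2.5.1 states the role of the measure: "Incidence and severity of TEAEs is the Secondary endpoint". It then defines the term. An adverse event "is considered TEAE to a given treatment if the event start date is on or after the treatment period start date", with the end of the study as the upper limit. The definition contains nothing on a rise in grade or a change to serious. SAP 5.5.1 builds the TEAE tables on it (system organ class, preferred term, severity, relationship) and plans no separate table of pre-treatment AEs that worsened. The protocol uses the term TEAE but does not define it, and SAP Section 7 lists no change on this point.

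AE collection starts earlier than treatment. Protocol 8.4.1 says that active collection "begins from the time the participant provides informed consent", and Protocol 8.3 says: "All participants will be monitored continuously for AEs from screening until the safety follow-up visit on Day 42". Table 1 of the protocol allows up to 42 days of screening, which includes an EGD with biopsy.

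Protocol 10.3.1 lists among events that meet the AE definition: "Exacerbation of a chronic or intermittent preexisting condition, including an increase in either frequency and/or intensity of the condition". The first study-drug risk in Protocol 2.3.1 is: "Potential for exacerbation of gastrointestinal symptoms associated with CeD".

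**The concern.** The listed risk is one of worsening, while the TEAE rule recognises only new onset. A participant who enters Day 1 with a recorded, ongoing symptom can become clearly worse after an infusion. If the event keeps its screening start date, the participant is absent from that preferred-term row and the post-dose grade is absent from the severity table.

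The effect is to understate incidence and maximum grade in the secondary safety endpoint, for just those participants in whom exacerbation would show. Because the documents do not say how a worsened AE is entered, the same clinical course may be counted at one site and not at another. Protocol 2.2.3 reports that GI AEs affected more participants on KAN-101 than on placebo in the first-in-human study, so this comparison needs a sound definition.

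**Working it through.** The plan gives no figure to reproduce. The check is whether any text supplies a worsening criterion or a new start date.

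**Step 1: apply the rule to one course of events.** Take a hypothetical nausea AE that starts at Grade 1 on Day -10, is ongoing at Day 1 and reaches Grade 3 after an infusion.

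| How the site enters it | Start date tested | TEAE under SAP 2.5.1? | Grade in TEAE severity table |
|---|---|---|---|
| One record, grade updated | Day -10, before Day 1 | No | None |
| New record at worsening | Day 1 or later | Yes | Grade 3 |

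Data entry alone decides the classification. The grades are illustrative: Protocol 2.2.3 reports no Grade 3 TEAEs in the first-in-human study.

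**Step 2: see whether the documents choose between the rows.**
- Protocol 10.3.1 makes exacerbation of a pre-existing condition an AE. For a symptom held as medical history, this leads naturally to a new AE with a post-dose start. For an AE already recorded in screening, the text does not say whether a second record is opened.
- Protocol 10.3.3, on follow-up, says: "New or updated information will be recorded in the originally submitted documents". This leans towards one record. It is weak evidence, because the next item concerns SAE updates to the safety group, so it may not govern CRF start dates.
- Protocol 10.1.7 refers to a CRF completion document, and SAP 5.5.1 refers to sponsor reporting standards. Neither is available here.

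The choice is left open, and the SAP's own definition does not cover the first row of the table.

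**Step 3: size.** Planned enrolment is 26 treated participants per arm. One participant is 1/26 = 0.038, or 3.8 percentage points of incidence in an arm. The expected number affected in an arm would be

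26 × (share with an AE ongoing at Day 1) × (share of those who worsen) × (share of those kept in one record).

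The documents give none of the three shares, so the product cannot be evaluated. A participant who has any other TEAE still counts in the overall TEAE row, so the loss falls mainly on preferred-term rows and maximum grade.

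**Step 4: the Day 1 boundary.** The rule compares dates, so an event on Day 1 before the infusion counts as treatment-emergent. SAP Appendix 2.1, Tables 4 and 5, separates pre-dose from post-dose for vital signs and laboratory tests. SAP 2.5.1 makes no such split for AEs. This over-counts, opposite to the main point, and is minor.

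**The case against.** The strongest reply is that Protocol 10.3.1 already treats an exacerbation as an AE in its own right. A site that follows it may enter the worsening with its own onset, and the start-date rule then works. This stands as a limit: the gap is conditional on the event staying in its original record. It does not close the gap, because nothing requires the second entry for an AE already open from screening.

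The group at risk is also probably small. Protocol Appendix 3 keeps expected symptoms of the disease under study from being AEs unless they are more severe than expected. Participants must have followed a gluten-free diet for at least 12 months, have negative or weak-positive serology and have a Vh:Cd of 2.3 or more. Uncontrolled IBS is excluded. The documents do not show that ongoing GI AEs at dosing are common in this population. This part stands.

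Worsening is visible elsewhere too. SAP 5.5.1 summarises and lists SAEs without restricting them to TEAEs and lists discontinuations due to AEs. SAP 5.3.2 analyses change in daily CDSD scores from a pre-Day 1 baseline. This stands in part. The CDSD does not cover every listed symptom (headache, dizziness and skin rash are not among its items), and its main analysis is on the FAS, which omits anyone who did not receive all three doses.

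A reader might infer a sizeable loss by supplying rates. If 15% enter with an ongoing GI AE and half of those worsen, 26 × 0.15 × 0.5 = 1.95 participants, or 7.5 points. Both rates are assumptions. Taking 10% to 20% and 25% to 75% instead gives 0.65 to 3.9 participants, or 2.5 to 15 points. The answer only reflects the inputs, and all of these figures assume that no site opens a new record.

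**Conclusion.** The definition is incomplete and should be corrected. As written, SAP 2.5.1 omits from TEAE incidence and severity any screening-onset AE that is ongoing at Day 1, worsens after dosing and is kept in its original record. Neither document prevents that form of recording.

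The size is unknown and probably small, at 3.8 percentage points per affected participant in an arm of 26. What is lost is mainly non-serious worsening.

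Two stronger readings are not supported. One is that every worsened screening AE is lost, which fails because a site may enter the exacerbation as a new AE. The other is that the trial would miss the GI risk of KAN-101, which fails because SAE summaries and CDSD scores show part of it. The conclusion assumes that the CRF completion document and the sponsor's reporting standards, which are not available here, do not already contain a worsening rule. If they do, the SAP should still state it.

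**What to change.** Replace the definition in SAP 2.5.1 with wording to this effect:

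> An AE is treatment-emergent if it starts at or after the start of the first infusion and before the end of the study, or if it started earlier and increases in CTCAE grade or becomes serious at or after the start of the first infusion. It is tabulated at its worst post-dose grade.

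Tying the rule to the start of the first infusion also settles the Day 1 boundary.

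Add a CRF completion note that a post-dose grade increase in an AE already open is entered as a new AE record with its own start date. The worst post-dose grade cannot be derived without this or dated grade changes, so the SAP sentence alone is not enough if the CRF holds one grade per AE. SAP 5.5 counts participants, so a second record under the same preferred term does not inflate the table.

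The cost is one SAP sentence, one data-entry instruction and a few more TEAE rows. Records already entered may need a query to date the increase. The rule is best fixed before safety data are seen by arm.

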#### Study KAN-101-01

In Study KAN-101-01 administration of KAN-101 was effective at inducing T-cell tolerance (Murray et al, 2023):

- Three doses of KAN-101, administered 3 days apart, at 0.15, 0.3 and 0.6 mg/kg dose levels was effective in inducing T cell tolerance to gliadin. KAN-101 treated participants exhibited minimal change or a decrease in the gliadin-specific T-cell response following GC while placebo patients exhibited an increase in the gliadin-specific T-cell response following GC.

CONFIDENTIAL

- KAN-101 also modified the immediate immune reaction upon ingestion of gluten by CeD participants in a dose-dependent manner. Participants treated with 3 doses of 0.6 mg/kg KAN-101, administered 3 days apart, exhibited lower median plasma IL-2 levels within hours of GC compared to placebo or 0.15 and 0.3 mg/kg KAN-101 dose levels.

KAN-101 demonstrated an acceptable safety and tolerability profile after single and multiple doses at all dose levels tested in KAN-101-01. There were no deaths, SAEs, or Grade 3 TEAEs observed. TEAEs were consistent with CeD participants upon gluten ingestion (ie, nausea, emesis, abdominal pain, headache, and diarrhea). No clinically relevant trends were observed for changes in vital signs, physical examination, laboratory tests, or ECG results. There were no meaningful correlations between the frequency of TEAEs and study drug dose level. There was an increased frequency of participants who experienced GI AEs in the total drug-treated group than in the placebo group in KAN-101-01. No MTD of KAN-101 was identified and no meaningful safety differences were observed among treatment groups during the study.

Data from the KAN-101-01 study suggests rapid elimination with mean half-life ranging from 3.74 to 36.8 minutes across 0.15 mg/kg to 1.2 mg/kg doses, following single or repeat IV infusions of KAN-101. The mean KAN-101 maximum exposure ( $C_{max}$ ) and systemic exposure (AUC) appeared to exhibit approximate dose proportionality across 0.15 to 1.2 mg/kg dose range. With repeat dosing, there was no accumulation of KAN-101 which was in concordance with the rapid elimination.

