Study Procedures		
KAN-101-03 includes a multiple-day (Day 15-28 daily) GC comprising ingestion of 9g/day of gluten protein.	Known AEs associated with GC are expected, which may include and are not necessarily limited to AEs of headache, fatigue/lethargy, nausea, vomiting, abdominal pain, diarrhea, constipation, and skin rash.  Histological damage will occur as a result of the prolonged GC and could result in altered absorption of nutrients or fluids. Symptoms of such damage could include diarrhea, weight loss, and iron deficiency anemia.	Participants will consume the GC in clinic on Day 15 and at home for the remain 13 days through Day 28 and will be monitored for AEs associated with GC and managed according to established standard of care.  The histological damage does not persist long-term and is reversed upon GFD. Participants will be monitored for AEs, including symptoms of CeD and intestinal mucosal damage, and safety labs will be assessed throughout the study to identify any abnormalities that may occur.
KAN-101-03 includes 2 EGD with biopsy (Screening and Day 29).	EGD with biopsy carries a small risk of bowel perforation. Duodenal biopsies also carry the risk of duodenal hematoma.	EGD for the study will be performed by qualified and experienced gastroenterologists.
Other		
The COVID-19 pandemic may pose risks to study participation.	Participants may have increased risk of SARS-CoV-2 infection by undergoing a study procedure at a study facility.	Inclusion of COVID-19 specific screening procedures and assessments according to the SoA .

CONFIDENTIAL

CT02-GSOP Clinical Protocol Template Phase 1 2 3 4 (14 April 2023)

Page 32

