## 4. STUDY DESIGN

### 4.1. Overall Design

Study KAN-101-03 is a multi-center, double-blind, placebo-controlled Phase 2a study to examine whether KAN-101 confers protection from GC-induced histological changes in the duodenum and to further evaluate the safety/tolerability of KAN-101 in adult participants  $\geq 18$  years to 70 years with CeD. Fifty-two participants (26 participants per arm) will be randomized 1:1 to the following arms:

1. 0.6 mg/kg KAN-101 (Arm 1)
2. Placebo (Arm 2)

Kanyos Bio, Inc. a wholly owned subsidiary of Anokion, as the sponsor of the study, is delegating to Pfizer all obligations for conduct of Study, including responsibility for preparing the protocol, and overall conduct and oversight of the study, including contracting with study sites. For this study, a DSMB (see [Section 10.1.5](#)) will review cumulative safety data.

This study comprises 4 periods:

- **Screening period:** up to  $\leq 42$  days before treatment initiation
  - During the screening period, eligibility will be confirmed by EGD with duodenal biopsy. The EGD with biopsy will only be performed once all other inclusion criteria are fulfilled. Histology results must be received prior to dosing to confirm eligibility.
- **Treatment period:** The study treatment period is 7 days (Day 1 to Day 7). Study intervention (either KAN-101 or placebo) will be administered to enrolled participants in the clinic IV on Days 1, 4, and 7. Post infusion each treatment day, participants will be monitored in the clinic for at least 4 hours for adverse reactions.

- **Gluten Challenge (GC): 14 days**
  - Participants will undergo a 2-week GC in which they will ingest 9 g/day of gluten protein in the form of 12 g vital wheat gluten. All participants will return to the clinic Day 15 for the first day of the GC. The Day 15 GC will be performed in the clinic under supervision and blood samples will be collected at least 5 minutes prior to GC and 4 hours after the completion of the Day 15 GC for biomarker assessment. Materials will be sent home with the participant to complete the daily GC for the next 2 weeks (through Day 28). The study site will call the participant on Day 16 and Day 21 to collect data on any AEs and/or CM over the telephone. Symptom monitoring will be conducted via the eDiary.

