### **8.2.1. Gluten Challenge**

All eligible, enrolled participants that received all three doses of study intervention will undergo a 2-week GC at starting Day 15.

- Participants are required to fast for at least 6 hours (or overnight), except for water and any medications they might have previously been prescribed, prior to GC. This pertains to both the study clinic visit during which the GC is performed (see [SoA](#)) and the at-home GC.
- At the Day 15 study visit, a qualified staff member will prepare the GC.
- Participants will consume 9g of gluten protein PO in the clinic and the participant will be observed for at least 4 hours to monitor for hyperacute reactions requiring medical treatment and collection of biomarker samples.
- Materials will be sent home with the participant to complete the GC daily for the next 13 days.

Completion of the GC is defined as consumption of the entirety of the 9g GC within approximately 15 minutes.

- At the Day 15 visit, participants will consume the GC on site under the observation of site staff. Participants will complete the remaining days of GC at home and document the completion of the GC via the eDiary.

Compliance with the GC is defined as completion of all 14 days of the GC. Only participants fully compliant with the GC may be analyzed as part of the PPS (see [Section 9.3](#)).

Only participants who have completed at least 7 days of GC should undergo the second EGD with biopsy. For participants who:

- Continue in the study, the EGD with biopsy will take place at the Day 29 visit (see [SoA](#)).
- Discontinue early, the EGD with biopsy will take place at the ET visit (see [SoA](#)).

Any symptoms associated with the GC should be recorded as AEs (see [Section 8.4](#)). Any AEs associated with the GC study assessment are separate to AEs related to study intervention (KAN-101/placebo).

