#### Events NOT Meeting the AE Definition

- Any clinically significant abnormal laboratory findings or other abnormal safety assessments that are associated with the underlying disease, unless judged by the investigator to be more severe than expected for the participant's condition.
- The disease/disorder being studied or expected progression, signs, or symptoms of the disease/disorder being studied, unless more severe than expected for the participant's condition.
- Medical or surgical procedure (eg, endoscopy, appendectomy): the condition that leads to the procedure is the AE.
- Situations in which an untoward medical occurrence did not occur (social and/or convenience admission to a hospital).
- Anticipated day-to-day fluctuations of preexisting disease(s) or condition(s) present or detected at the start of the study that do not worsen.

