5.5.1. Adverse Events

Adverse events will be summarized for the SAS according to Sponsor's reporting standards for

- TEAEs
- Serious AEs (SAEs)
- TEAEs will be summarized by the number of participants reporting any TEAE, system organ class (SOC), preferred term (PT), severity, relationship to investigational product (based on investigator's judgement).
- CTCAE is used to grade the severity of AEs. TEAEs related to GC and infusion-related reactions (IRR) will also be summarized separately.
- SAEs will be summarized by SOC and PT, and individual SAEs will be listed by participant.

A list of subjects who prematurely discontinue from the study due to an AE will be provided as well.

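### The main TEAE tables are not split by onset before or after the first gluten challenge, so a dosing-period difference between arms can be diluted, and separating the two periods rests on investigator attribution

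*SAP*

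**What the plan says.** Incidence and severity of TEAEs is a secondary endpoint. SAP 2.5.1 treats an event as treatment-emergent "if the event start date is on or after the treatment period start date and before end of study". Protocol 4.1 places the infusions on Days 1, 4 and 7, the daily 9 g GC on Days 15 to 28, and the end of follow-up at Day 42.

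SAP 5.5.1 tabulates TEAEs in the safety analysis set (SAS) by system organ class, preferred term, severity and investigator-judged relationship to product. It adds that "TEAEs related to GC and infusion-related reactions (IRR) will also be summarized separately". No table by onset period is listed.

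Protocol 2.3.1 gives two symptom lists:
- For study intervention: "headache, dizziness, fatigue/lethargy, nausea, vomiting, abdominal pain, diarrhea, constipation, skin rash", followed by abdominal tenderness.
- For the GC: "headache, fatigue/lethargy, nausea, vomiting, abdominal pain, diarrhea, constipation, and skin rash".

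Under protocol 7.1, participants who withdraw from treatment without three full doses do not undergo the GC. SAP 3 keeps anyone who received any portion of study intervention in the SAS.

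On recording, protocol 8.2.1 says "Any symptoms associated with the GC should be recorded as AEs". The general list in Appendix 3 of events that do not meet the AE definition includes "The disease/disorder being studied or expected progression, signs, or symptoms of the disease/disorder being studied, unless more severe than expected".

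**The concern.** The safety objective concerns the tolerability of KAN-101. The TEAE window holds two exposures: three infusions that differ by arm, then a challenge given in both arms that is itself expected to cause GI symptoms, headache and fatigue. A participant with an event in either period counts once. If most participants in both arms have a GC event, the any-TEAE line and the common GI lines approach a ceiling, and a difference that arose before the GC has little room to show.

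The planned separate summaries sort events by judged cause, not by when they began. With nearly the same symptoms expected from both exposures, judged cause is a weak separator once the GC has started. Onset date does not depend on that judgement.

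At stake is whether the clinical study report can show directly how KAN-101 and placebo compare on adverse events before any gluten was given.

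**Working it through.** The documents state no AE rate, safety margin or safety power, so there is no planned figure to reproduce. Every rate below is an assumption.

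**Share of the window after the first GC.** Days 15 to 42 are 28 of 42 days: 28/42 = 67%.

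**Pooled incidence.** Let a be the risk of at least one event before the first GC and g the risk from the first GC onward. If the two are independent within a person, pooled risk = 1 − (1 − a)(1 − g). If g is the same in both arms, the pooled difference is (1 − g) × (a for KAN-101 − a for placebo). The pre-GC difference is thus shrunk by the factor 1 − g.

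Assume a = 40% on KAN-101 and 15% on placebo, a difference of 25 points, and vary g:

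| g, both arms | KAN-101 pooled | Placebo pooled | Difference |
|---|---|---|---|
| 30% | 1 − 0.60 × 0.70 = 58.0% | 1 − 0.85 × 0.70 = 40.5% | 17.5 points |
| 50% | 1 − 0.60 × 0.50 = 70.0% | 1 − 0.85 × 0.50 = 57.5% | 12.5 points |
| 80% | 1 − 0.60 × 0.20 = 88.0% | 1 − 0.85 × 0.20 = 83.0% | 5.0 points |
| 90% | 1 − 0.60 × 0.10 = 94.0% | 1 − 0.85 × 0.10 = 91.5% | 2.5 points |

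**Dependence between periods.** If the same people tend to have events in both periods (Gaussian copula, correlation 0.5), the last row becomes 91.0% versus 90.2%, a difference of 0.8 points.

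**Denominator.** If a fraction d of an arm's SAS never starts the GC, the GC-period incidence over the whole SAS is (1 − d) × g. An arm with more early dosing discontinuation therefore shows fewer GC events for that reason alone. The documents give no value for d by arm, so this is not quantified.

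**Other SAP data already cut at this point.** In Appendix 2.1, Tables 4 and 5 end the Day 15 window for vital signs and laboratory tests before the first GC. The weekly symptom diary (CDSD) periods in SAP 5.3.2 end Week 2 the day before the first GC. The TEAE tables have no such cut.

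**The case against.** The strongest reply is that the events are not simply merged. SAP 5.5.1 shows relationship to product and separately summarises GC-related events and infusion-related reactions, and protocol 8.2.1 keeps GC events apart from study-drug events. An event that starts before the first GC cannot be due to it, Appendix 3 tells investigators to weigh timing relative to dosing, and the reported mean half-life is 3.74 to 36.8 minutes. This stands as far as it goes. But no planned table isolates the pre-GC events. The relationship table spans both periods, and a pre-GC event judged unrelated to product appears only in pooled counts. That onset settles the question before the GC is a reason to tabulate by onset.

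Second, weekly CDSD scores compare the arms on GI symptoms and tiredness before the GC, so a GI excess could be seen there. That is a partial answer. The CDSD is an exploratory patient-reported outcome, not AE incidence or grade. Its main analysis is in the full analysis set, which drops participants without all three doses or at least 7 GC days. SAP Appendix 1 lists a CDSD analysis in the SAS, while the table in SAP 5 lists none.

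Third, a 90% background is a choice that suits the point. Individual preferred terms may be much less common, and at 30% most of the difference survives. This is fair, and the table above shows the range.

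Fourth, safety analysis is descriptive, listings are produced, the DSMB reviews cumulative data, and tables follow sponsor standards that the documents do not reproduce. Those standards might already include an onset split, but the SAP does not say so.

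A reader might also take the first-in-human finding, "There was an increased frequency of participants who experienced GI AEs in the total drug-treated group than in the placebo group", as evidence of a dosing-period excess. The protocol does not support that reading. It does not say when those events arose, that study also included a GC, the TEAEs are described as consistent with gluten ingestion, and no meaningful safety differences among groups were reported. The finding makes a by-period table informative; it does not supply a rate.

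**Conclusion.** The point holds as a gap in presentation. The main TEAE tables pool the dosing and GC periods, and the separation that is planned rests on attribution between two exposures with nearly the same expected symptoms. Dilution follows from arithmetic: with equal GC risk in both arms, a pre-GC difference is multiplied by 1 − g, so 25 points become 17.5 at g = 30% and 2.5 at g = 90%. These sizes assume independent periods and illustrative rates.

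A reader might infer more, namely that pooling would hide harm or make it look like benefit. With assumed GC risks of 60% on KAN-101 and 85% on placebo, the pooled figures are indeed 76.0% versus 87.25%. But that requires KAN-101 to lower GC adverse events. The documents treat the effect on symptoms as exploratory and state no size. The reduction needed also depends on the background. The break-even KAN-101 GC risk is 1 − 0.85(1 − g)/0.60, with g the placebo risk. It is 85.8% when placebo is 90%, but 0.8% when placebo is 30%. Reversal is possible under some assumptions and is not shown by the documents.

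The two recording statements (protocol 8.2.1 and Appendix 3) are a separate, lesser point. Protocol 8.2.1 is specific to GC symptoms, Appendix 3 also counts exacerbation of a pre-existing condition as an AE, and section 8.4.7 marks disease-related events that do not qualify as AEs as not applicable. That sites would count events differently is conjecture, but the texts should agree.

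**What to change.** Keep the overall TEAE table. In SAP 5.5.1, add TEAE tables (any event, system organ class and preferred term, grade, relationship) by arm and onset period:
- (a) first dose to before the first GC, with the SAS as denominator;
- (b) first GC onward, with participants who started the GC as denominator.

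Define the cut by each participant's actual first GC, as Appendix 2.1 does for laboratory tests and vital signs. For events that start on the first GC day, use onset time or state a rule for assigning the period.

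Separately, reconcile protocol 8.2.1 with the Appendix 3 text on expected disease symptoms.

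The cost is SAP wording, extra table columns and one clarifying line in Appendix 3. The analysis needs only AE onset and GC dates, plus onset time if that is the rule chosen for the first GC day. The downside is longer safety tables.
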